The main mechanism of action of GLP-1 is to increase glucose-mediated insulin release, delaying gastric emptying, and inhibiting glucagon release. GLP-1 agonists have been shown to promote satiety¹⁵, leading to weight loss. GLP-1 is secreted within minutes of food intake by L-cells, located in the distal ileum and colon. Oral (but not IV) glucose administration causes GLP-1 secretion¹⁶. Additionally, GLP-1 readily crosses the blood brain barrier where it is thought to regulate ingestive behavior in the hypothalamus, which subsequently has direct effects on gastric emptying and resultant satiety¹⁵. GLP-1 is secreted 15 to 30 minutes after food intake and is there measured at multiple time points post-prandial¹⁷. Additionally, GLP-1 has been shown to increase following other weight loss interventions such as gastric bypass, with significant changes seen as early as 6 weeks¹⁷.

This connection has led to attempts at manipulations of the gut microbiome in order to modulate this process¹⁸. In a recent trial, obese diabetic patients received a fecal microbiota transplantation (FMT) from either lean donors or autologous stool¹⁹. Those in the treatment group were noted to have improved peripheral and hepatic insulin sensitivity. FMT involves the transfer of donor stool to a recipient. It has become widely accepted as a treatment for recurrent *Clostridium difficile* infection (CDI), with a cumulative cure rate of >90% and minimal adverse events²⁰. These preliminary studies suggest that FMT using lean donor stool may be

used to treat obesity and its sequela. **We hypothesize that for obese patients, induction and maintenance FMT utilizing lean donor stool will correct a dysbiosis that has led to a decrease in circulating GLP-1 which acts as a surrogate marker for weight loss.**

II. SPECIFIC AIMS

Specific Aim 1: Assess the safety of FMT in patients with obesity.

Hypothesis: Induction FMT followed by weekly maintenance capsule FMT will be safe and well tolerated by obese patients.

Specific Aim 2: Assess GLP-1 as a therapeutic biomarker for clinical response to fecal microbiota transplantation

Hypothesis: Fecal Microbiota Transplantation will lead to an increase in SCFA which will lead to an increase in the metabolic regulator GLP-1.

Specific Aim 3: Determine the impact of fecal microbiota transplantation on the intestinal microbiome of patients with obesity via 16s ribosomal RNA sequencing.

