Hypothesis: Fecal microbiota transplantation will result in a sustained repopulation of the patient's microbiome that corresponds to the bacteria from the donor stool.

III. Methods and Study Design

This is a randomized controlled pilot study to assess the safety and to measure the microbiological and clinical impacts of FMT in patients with obesity. We will continue to prospectively enroll and screen adult patients until 20 patients have completed all study visits. We anticipate total enrollment to be 50 patients to account for screen fails and dropouts. Eligible patients are those who are obese (BMI of 35 kg/m² or greater). Patients will be randomized 1:1 to receive FMT or placebo. The participants will receive either an FMT from a lean healthy donor using 30 induction FMT capsules or placebo capsules. The participants will continue to receive a monthly maintenance dose of 12 FMT oral capsules or placebo at week 4 and week 8. Serum for hormone levels will be collected at baseline, weeks 1, 4, 6, 8 and 12. Stool for microbial assessment will be collected at baseline and weeks 1, 4, 6, 8, 12, 26, and 52. A Food Frequency Questionnaire will be taken by the patient at week 0. Donor Stool will be obtained from OpenBiome. OpenBiome is a nonprofit 501(c)(3) organization that provides hospitals with screened, filtered, and frozen material ready for clinical use (See Attachments for OpenBiome Quality and Safety Program as well as donor screening examples).

Primary Safety Endpoint:

Safety Endpoints: Number and nature of adverse events at week 1, 6, 12 and 26.

Primary Clinical Endpoint:

The primary clinical end point is an increase in the AUC for GLP-1 after a mixed meal test from baseline and 12.

Secondary Endpoints:

- Microbial Endpoints: Recipients fecal microbial diversity at week 6 and 12 compared to baseline
- Clinical Endpoints: Decrease in BMI and waste circumference at week 6 and 12 compared to baseline.

Trial Treatment:

The treatment for this trial will be administration of an induction dose of 30 FMT capsules ingested orally. Treatment will occur after screening.

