Subsequent FMT administration will be maintenance capsules of frozen FMT material ingested orally every 4 weeks (weeks 4 and 8). All ingestions will be undertaken in the clinic under supervision. A follow-up phone call will be undertaken 4 hours after each ingestion visit to screen for adverse events. At 48 hours and 24 hours prior to and the day of each capsule dose (regardless of group) the patient will take a single dose of 20mg of omeprazole.

Dosage Form

1. Initial dose - filtered solution of donor stool in 30 gelatin capsules at Day 0 (16500µl total).
2. Maintenance dose – twelve capsules of fecal material taken every 4 weeks (550µl of fecal material in each size 00 gelatin capsule)

Dosing Regimen

Single induction dose of 30 capsules (16500µl)

Monthly dose of 12 capsules of fecal material (total 6600µl of fecal material at week 4 and week 8)

Capsule preparations are delivered to clinical investigators in double containment shipping vessels packed with dry ice, as with non-encapsulated placebo preparations. Packaging is labeled with the same information included on non-encapsulated preparations, with the addition of a clause instructing clinicians to administer the material to patients within 90 minutes of removal from frozen storage. Patient instructions listed in Appendix 6.

Packaging

Encapsulated fecal material in freezer safe bottles will be stored in Styrofoam boxes from the Microbiome Health Research Institute at Massachusetts Institute of Technology, as described in their Drug Master File (15543).

The Placebo Treatment:

Those in the placebo arm will undergo procedures as in the active arm. They will be given 30 placebo capsules at time of induction (Day 0) and this will be followed by 12 placebo capsules each month.

Placebo Oral Capsules

Placebo capsules are prepared to support randomized, placebo-controlled studies of FMT. These capsules are prepared according to the specifications described below and utilized in studies as indicated by the study IND.

1. An autoclaved solution consisting of 80% cocoa butter, 20% glycerol and brown food coloring, without the addition of human stool, is used as a placebo control.
2. The autoclaved placebo solution is transferred to a reservoir.
3. Capsules are generated as outlined in 6-9 of section V above.
4. Each capsule is visually inspected for integrity and contamination of the outer surface. Capsules passing inspection are placed into an HDPE plastic bottle for immediate storage at -80°C.

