Symptom diary Cards will be filled out weekly for adverse event monitoring

Week 4, 8 (Treatment and Control Arms): Monitored Capsule Consumption and Follow-up study visits for assessment of:

- Ingestion of 12 FMT capsules or inactive placebo.
- A proton pump inhibitor will be taken daily for the 48 hours 24 hours prior to and day of capsule consumption.
- BMI, Iliac measurements, hip to waist ratio
- Stool for microbiome analysis and metabolomics
- CBC, LFTs, FBG, HgA1C, lipids, glucose, metabolomics
- diet recall
- Symptom diary Card and Adverse Event screening

Weeks 6, 12 : Follow-up study visits for assessment of:

- BMI, Iliac measurements, hip to waist ratio
- Stool for microbiome analysis and metabolomics
- CBC, LFTs, FBG, HgA1C, lipids, glucose, metabolomics, ghrelin and leptin, PYY and adiponectin
- Mixed meal tolerance test followed by serum for GLP-1, Leptin and PYY at time 0, 15, 30, 45, and 60
- diet recall
- Indirect Calorimetry
- Symptom Diary Card and Adverse Event screening

Week 26 and 52:

- Safety assessment and Symptom Diary Cards via phone interview by a physician to screen for adverse events.
- Stool sample for microbiome analysis to be mailed in
- Ask for the patients current weight

Stool collection instructions are outlined in Appendix 2.

Patient obligations in the study will end at week 52 however the patient's medical record may be followed prospectively for evaluation of weight loss and weight loss surrogates as well as metabolic parameters done for clinical care through year 5 post-enrollment as needed. This may include review of partner's available records or records from home provider. (when applicable)

Stopping Criteria

Adverse events will be specifically monitored at week 1, 4, 6, 8, 12, 26, and 52 after FMT by direct patient interviews, or by reporting from clinical sites of adverse events at any time in-between. A data safety and monitoring board (DSMB, Appendix 5) will review all patient data to ensure optimal patient safety and precautions for subjects with obesity treated with FMT. A severity grade for adverse events (Appendix 6) and subject symptom diary cards will be used (Appendix 7). The DSMB will meet a minimum of 2 times: after treatment of the first 10 subjects, and after treatment of all 20 subjects. Study will be stopped under the following circumstances;

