Patients will be asked to document their symptoms using the symptom diary card (Appendix 5) as a memory aide. Subjects will be asked to complete a symptom diary card at baseline, prior to FMT, and on the day of treatment to assess their baseline. They will then be asked to complete a symptom diary card each day for 1 week post-FMT and then once a week thereafter for 12 weeks and then during follow-up at weeks 26 and 52. The symptom diary card will help the patient monitor and keep track of adverse events and will be reviewed by the Principal Investigator.

In addition the DSMB may convene additional meetings if necessary to ensure the ongoing monitoring and safety of the subjects treated with FMT. The internal DSMB will include the following individuals: [name] (BWH Gastroenterology, Chair), [name] (Gastroenterology – BWH) and [name] (Pulmonology/Ethics-BWH). All events will be reported directly to the DSMB and the Institutional Review Board (IRB) in accordance with Harvard University policy: Investigators will promptly report to the IRB all unanticipated problems involving risks to human subjects or others under Title 21 of the Code of Federal Regulations (21 CFR) part 56 (Institutional Review Boards), part 312 (Investigational New Drug Application), and part 812 (Investigational Device Exemptions).Harvard Medical School policy is consistent with guidance set forth by the Office for Human Research Protections (OHRP) (presented January 15, 2007) <http://www.hhs.gov/ohrp/policy/AdvEvntGuid.htm> and the FDA (presented January 14, 2009) <http://www.fda.gov/downloads/RegulatoryInformation/Guidances/UCM126572.pdf> when determining what related events require review by the Institutional Review Board. Any serious AEs also will be evaluated by the DSMB for review and determination of whether the trial should continue.

All subjects will be followed for an additional six months following the end of their treatment. Subjects that did not experience a AEs or SAEs will receive a telephone call to monitor their current symptoms and quality of life. For subjects that did experience a AE or SAE that was found to be connected to the FMT treatment, we ask that they return to our medical center for an exam with their gastroenterologist. All treatment and outcome of AEs will be documented on the CRF and summarized in the CSR. All AEs will be followed to resolution or stabilization by the study physician.

VIII. Biostatistical Analysis:

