Appendix 5.

Fecal Microbiota Transplantation - Record of Side Effects

This diary is one way researchers will get information from you regarding any possible problems or side effects in this study.

- ❖ **What you are going to do is simple.** Just keep a record of any unpleasant thing that happens to you while you are in the study, before, during, and after we have completed the stool transplant. We even want you to record things that do not seem to be part of the stool therapy, at all.
- ❖ **When do you start? When do you end?** You will record one entry 1-week prior and on the day of the transplant. You will then complete one entry per day for the first week following the treatment and then once a week thereafter for 12-weeks.
- ❖ **What do you look for? What do you report?** Any symptom or problem whether or not it may be from the medicine, stool therapy. This could include: fever, abdominal pain, a big belly, lots of gas, diarrhea, nosebleeds, and anything else you know is not quite right.
- ❖ **What will you do?** In the first 7 days after the transplant, you will report some of the specific things that have bothered you by checking the boxes in the diary (see below). You can also write any other problems that you may have had during that time. **Additionally, you will record your temperature once for each day for the first 7 days after the transplant, unless you feel hot. If you feel hot, please take your temperature again.**
Please make sure to record the highest temperature taken that day if you take it more than once.

Continue to record any problem up to 6 months after the transplant.

How will you record it? Like this...

EVENT	DATE OF ONSET	INTENSITY	ACTION TAKEN	MEDICATION	DATE RESOLVED
Fever	3/1/12	3	Missed 2 days of school	Tylenol-200mg	3/3/12
Sore throat	3/5/12	1	None	None	3/6/12

OTHER SYMPTOMS

Record each symptom at its **worst** level for each day.

For example, a sore throat that starts at 'Grade 1' but increases to 'Grade 2' should be recorded as 'Grade 2'.

Examples of Grades:

Grade 1 – Mild: I noticed the symptom. It did not keep me from doing my normal activities.

Grade 2 – Moderate: I noticed the symptom and it kept me from doing some of my normal activities.

Grade 3 – Severe: I really noticed the symptom and it kept me from doing activities that I wanted or needed to do.

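### As most naturally read, daily symptom cards and temperatures follow only the induction dose, so mild, short-lived events are captured less sensitively after the week 4 and week 8 doses

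*Combined protocol and SAP*

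**What the plan says.** There are three administrations. After induction at week 0, Section III says: "The participants will continue to receive a monthly maintenance dose of 12 FMT oral capsules or placebo at week 4 and week 8".

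The recording rules are in three places:

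- Section VII asks participants to "complete a symptom diary card each day for 1 week post-FMT and then once a week thereafter for 12 weeks", with further cards at weeks 26 and 52.
- Section IV.A, under Weeks 2-12, says: "Symptom diary Cards will be filled out weekly for adverse event monitoring".
- Appendix 5, the diary itself, says: "You will then complete one entry per day for the first week following the treatment and then once a week thereafter for 12-weeks". On temperature it says: "you will record your temperature once for each day for the first 7 days after the transplant". It ties the symptom checkboxes to the same 7 days.

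Other safety contacts apply to every dose. Section III (Trial Treatment) says "All ingestions will be undertaken in the clinic under supervision" and "A follow-up phone call will be undertaken 4 hours after each ingestion visit to screen for adverse events". Sections IV and VII add adverse event interviews at weeks 1, 4, 6, 8 and 12, and reports at any time in between.

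Section VIII makes safety the main objective. The Aim 1 hypothesis in Section II covers the whole regimen: "Induction FMT followed by weekly maintenance capsule FMT will be safe and well tolerated by obese patients". The primary safety endpoint in Section III is the number and nature of adverse events at weeks 1, 6, 12 and 26.

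**The concern.** The diary wording suits a single transplant, but the trial gives three. Each maintenance dose is a new exposure to donor material, and together the two make up 24 of 54 capsules. The known risks listed in Section IX (altered bowel pattern, cramping, belching) can be mild and brief, so how often recording takes place affects what is seen.

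If recording is dense after induction and thin afterwards, a lower event count after weeks 4 and 8 has two possible explanations: better tolerance on repeat dosing, or fewer recordings. The data could not separate them. The endpoint weeks add to this, because weeks 1, 6 and 12 fall 1, 2 and 4 weeks after the most recent dose.

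**Working it through.** The plan gives no detection standard, event rate or power figure to reproduce. The check is a count of scheduled recordings by dose.

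**Inputs.** Doses on days 0, 28 and 56 (Section III). Interview visits on days 7, 28, 42, 56 and 84 (Sections IV and VII). Daily cards on days 1 to 7 (Section VII, Appendix 5). Weekly cards at weeks 2 to 12 (Section IV). Cards completed before or on the day of treatment are left out.

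| | Week 0 | Week 4 | Week 8 |
|---|---|---|---|
| Supervised ingestion and 4-hour call | yes | yes | yes |
| Cards in the 7 days after the dose | 7 | 1 | 1 |
| Temperatures under the daily instruction | 7 | 0 | 0 |
| Cards to the next dose, or to week 12 | 10 | 4 | 4 |
| Days to the next interview visit | 7 | 14 | 28 |

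The card has a field for the day's highest temperature, so a weekly card may still hold one reading. Scheduled readings of temperature and stool count after a maintenance dose are thus about 1 day in 7.

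**Why those two fields matter.** Appendix 4 grades fever by measured temperature. It grades diarrhea partly by the increase in stool number, with grade 3 stated per 24 hours. On the Appendix 5 card both are single-day entries.

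**Share of exposure.** Maintenance is 2 × 12 = 24 of 30 + 24 = 54 capsules. By volume it is 24 × 550 = 13,200 of 54 × 550 = 29,700 µL, or 44%. This is a share of the material given, not of events missed.

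**Scale against sample size.** Twenty completers at 1:1 give about 10 on FMT. With 0 events in 10, the one-sided 95% upper limit for the event rate is 1 − 0.05^(1/10) = 25.9%. If a method detects a fraction *s* of events, the limit becomes 25.9%/*s*. The documents give no *s*; assumed values show the range:

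| Assumed *s* | Upper limit with 0 of 10 recorded | Chance of recording at least one event if the true rate is 10% |
|---|---|---|
| 1.0 | 25.9% | 65% |
| 0.9 | 28.8% | 61% |
| 0.75 | 34.5% | 54% |
| 0.5 | 51.8% | 40% |

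The last column is 1 − (1 − 0.10*s*)^10.

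**Effect of restarting the daily diary.** Cards in the 7 days after each dose go from 7/1/1 to 7/7/7, and daily temperatures from 7/0/0 to 7/7/7. Fourteen daily cards replace 2 weekly ones, so the total rises by 12, from 7 + 11 = 18 to 21 + 9 = 30. Visit timing does not change.

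**The case against.** The strongest reply is that the diary is only one instrument, and not just a one-day snapshot. Section VII describes it as an aid to memory. The card has columns for onset, intensity, action and resolution, and Appendix 5 tells participants to note anything unpleasant and to go on recording problems for 6 months. Cramping two days after the week 4 dose is therefore reportable whichever day the weekly card falls. Interviews at weeks 6, 8 and 12, in-between reports, supervised dosing and the 4-hour call add to this. Closest watch after first exposure and the largest dose is also a defensible choice. All of this stands.

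It rules out three stronger readings that a reader might infer:

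- That a one-day event after a maintenance dose has only a 1-in-7 chance of being captured, and a two-day event 2 in 7. Those fractions apply at most to the measured temperature and stool count, and only if the card day is random. They are not capture rates for adverse events.
- That the maintenance doses go unwatched, so Aim 1 cannot be supported. The documents set no detection standard, Aim 1 concerns the regimen as a whole, and about 10 FMT completers would limit any safety conclusion even with perfect capture.
- That the FMT-placebo comparison is biased. Both arms follow the same schedule, so it creates no difference in ascertainment between them.

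The plan also states no comparison of event rates between doses. But it does not rule one out, and counts reported by week invite it.

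Finally, the text does not define which dose starts the daily week, and the Appendix 1 timeline cannot be read in the copy available. A restart after each dose cannot be wholly excluded, although the weekly rule for weeks 2 to 12 argues against it. If a restart is intended, the wording still needs to say so.

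**Conclusion.** The point holds as a limited, inexpensive improvement. On the natural reading, recording in the week after a dose falls from 7 cards to 1 for two of the three administrations, and the gap to the next interview lengthens from 7 days to 14 and then 28. Serious or lasting events would probably still be found. What is lost is sensitivity to mild, short-lived events, chiefly those graded on measured temperature or stool count, and the ability to compare event counts between induction and maintenance doses.

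How much sensitivity is lost cannot be estimated from the documents. The conclusion assumes that the daily week belongs to the Day 0 dose and that participants complete the cards as scheduled.

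**What to change.** In Section VII, in the Weeks 2-12 text of Section IV and in Appendix 5, state that the daily card and daily temperature run for 7 days after each capsule administration (weeks 0, 4 and 8) in both arms, with weekly cards otherwise. Plan to report adverse events by arm and by time since each dose.

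The cost is revised protocol and diary wording and about 12 more one-page cards per participant. No visit, staff or procedure is added. The downside is slightly more burden for participants and more mild events on record.

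If the daily diary is not restarted, say so, and state that adverse event rates will not be compared between induction and maintenance doses.

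Two inconsistencies should be reconciled in the same edit. Aim 1 describes maintenance as weekly, whereas Section III gives it at weeks 4 and 8. The end of diary recording also differs between Section IV (week 12), Section VII (12 weeks after the first week, then weeks 26 and 52) and Appendix 5 (12 weeks for scheduled entries, 6 months for any problem).

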Appendix 1:

Appendix 2.

Stool collection Instructions

Important note about sample collection and shipping:

Collect and ship your stool samples by FedEx according to the Samples Collections Schedule that your research coordinator explained to you. Please ship within 24 hours of collection. Please contact your research coordinator, [name] [name] if you have any questions.

This kit contains the supplies needed for 1 stool sample collection and 1 return shipment.

Part 1 — Preparation for one collection

1. Each kit contains the following stool collection materials (see photo):
 - 1 Blue Bowl + Seat to collect your stool
 - 1 Tube with a screw cap top (a Para-Pak vial). This tube has a built-in spoon for scooping and contains a liquid that is a preservative solution
 - 1 Pair of gloves for hygienic collection
 - 1 Plastic dropper [optional use]
2. Wash your hands with soap and water, then rinse.
3. Urinate into toilet BEFORE stool collection.

Part 2 — Collection Seat Placement

1. Lift toilet seat.
2. Place Blue Bowl and Seat at the back of the toilet bowl for collection.
3. Lower toilet seat and ensure stability of the blue collection bowl.
4. Deposit stool directly into the blue collection bowl.

